Evidence suggests that culturally-tailored interventions may increase cessation in AIs but face-to-face delivery is costly and hindered by lack of transportation among participants. Prior work by the American Indian Cancer Foundation (AICAF; subcontract on proposal), shows that references to traditional tobacco in cessation messages can positively affect self-efficacy to quit (unpublished data). To our knowledge, only two culturally-tailored cessation interventions for AI peoples exist that purposely engage AI voices throughout the research and utilized rigorous methodology (i.e., included a control group, biochemically confirmed abstinence). The first is the All Nations Breath of Life (ANBL) intervention which was created for AIs representing many tribes and included pharmacotherapy, in-person behavioral support led by AI facilitators, and culturally-tailored curriculum.¹⁰ Biochemically confirmed abstinence was higher in the tailored versus standard group, though the difference between the groups was not statistically significant (11% vs 7%).¹⁰ The second, a tribal-specific program which included pharmacotherapy, also observed higher, but non-significant, abstinence in the tailored versus standard group (23% vs 14%).¹¹ Both studies observed poor retention (~40% loss-to-follow-up) and lack of transportation was a major contributor. Innovative approaches that can reach AI smokers and, that overcome the barrier of travel to an intervention site are needed to address commercial smoking among AI people.

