4. **Exit Survey:** At the end of the day on the last day of the 5 weeks of app use (i.e., 5 weeks + 1 day), an automated survey link from REDCap will be sent to participants email to assess self-report outcome measures. Participants will also be called and texted to remind them to complete the survey.
5. **Optional end of study interview:** Those randomized to the tailored QuitGuide may be asked to participate in a follow-up interview to get their feedback on using the app. We expect asking up to 10 people to complete this interview.

All measures are displayed in the table:

Baseline survey collected via REDCap: Demographics, America Indian Identity Measures, Internet and smartphone use, Traditional Tobacco Use, Commercial Tobacco History, Nicotine Dependence Scale, Contemplation Ladder, Environmental Smoke Exposures, Health Literacy, Alcohol consumption, Financial Strain, Perceived Stress Scale, Brief Resilience Scale, Everyday Discrimination Scale
--

Data collected through using app and transferred from SmokeFree.gov:

All app user data. Any and all interactions with the app including days and frequency of use each day and which app components are accessed.
--

MEDICAL PROTOCOL (HRP-590)

PROTOCOL TITLE: QuitGuide for American Indians: Aims 2 & 3

VERSION DATE: 11-16-2022

Exit survey collected via REDCap: Contemplation Ladder TimeLine follow-back calendar to assess self-report CPD, use of any pharmacotherapy, 24-hour quit attempts, use of other cessation resources, Minnesota Nicotine Withdrawal Scale, Usability of App Design by System Usability Scale (SUS) Acceptability measures; plus open-ended responses on app
Audio recordings from the interviews among a subset of the participants
Saliva Sample

5.3 Study Duration:

- Individual participant duration is 5 weeks.
- The duration to enroll all study participants is 1.5 years.
- The duration for all data collection and analysis is 2.5 years.

5.4 Use of radiation:

The study does not use any radiation.

5.5 Use of Center for Magnetic Resonance Research:

The study does not use any CMMR resources.

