The objective of our primary analysis is to test the treatment effect on frequency of app initiated by the participant. Frequency of app initiated will be summarized by treatment group (tailored app vs standard app) using descriptive statistics, and analyzed using a Poisson regression model with covariates for treatment group and the three stratification factors (rural/urban clinic, male/female gender and <50 years of age/50+ years of age). Assumptions about mean and variance will be evaluated and if over-dispersion is present, negative binomial regression will be used. If data are zero-inflated, zero-inflated Poisson or negative binomial models may be considered.. This analysis will be performed using data for all participants who were randomized, while assuming non-use of app for those who did not complete the week 5 survey from the last day they launched the app.

Secondary Analysis

A secondary analysis of the primary endpoint will be performed that also adjusts for any other covariates that differ across treatment groups at baseline with a p-value less than 0.20 (covariates listed above). We acknowledge the limitations of this due to a small sample size and will take this into account when determining what additional covariates to adjust for. Additionally, a sensitivity analysis will be performed for all subjects who completed the week 5 survey.

Secondary and Exploratory Endpoint Analysis

Secondary and exploratory endpoints will be analyzed using the same approach as the primary endpoint. These endpoints will be analyzed using an appropriate regression framework (i.e. linear, logistic, Poisson etc.), adjusting only for baseline measurements of the endpoint, if available, and the three stratification factors (rural/urban clinic, male/female gender and <50 years of age/50+ years of age). Secondary analyses will consist of an adjusted analysis, as

MEDICAL PROTOCOL (HRP-590)

PROTOCOL TITLE: QuitGuide for American Indians: Aims 2 & 3

VERSION DATE: 11-16-2022

described above. All analyses will utilize residual plots and other diagnostic statistics to evaluate all modeling assumptions.

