Measures of the ability to abstain from smoking (self-reported 24-hour, 7-day and 30-day abstinence) will be analyzed using a similar approach to the primary and secondary/exploratory endpoints, and summarized using a binary endpoint. Continuous 7-day biochemically-verified abstinence (saliva cotinine < 10 ng/mL⁸) will be summarized for those who self-reported 7-day abstinence prior to the week 5 survey, and analyzed using logistic regression, with a main effect for treatment group and adjustment of the stratification factors (rural/urban clinic, male/female gender and <50 years of age/50+ years of age). Because traditional tobacco (depending on the method of use and plants used) and secondhand smoke can increase saliva cotinine, additional analyses may be performed to explore their impact on biochemically-confirmed abstinence. In addition, secondary analyses will consist of an adjusted analysis, as described in above.

Subgroup Analysis

No subgroup analyses will be performed due to small sample size.

Missing Data

An intent-to-treat analysis requires that subjects are analyzed according to their randomized treatment assignment, regardless of compliance to the study product, and that complete data are available on all study subjects. Every effort will be made to limit the amount of missing data in this trial, and study participants will be incentivized to partake in each study component, return the saliva sample, and complete all components.

We will compare subjects with and without missing data in order to identify baseline covariates associated with missing data. All observed data will be utilized in the analyses, with missing data being assumed to be missing at random. Sensitivity analyses of the secondary/exploratory endpoints using multiple imputation may be considered depending on the amount of missingness.

Interim Analyses

No planned interim analyses.

All statistical analyses will be performed by [name] from the Masonic Cancer Center, Biostatistics Core.

15.2 Power Analysis:

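### Exit-survey ratings and abstinence are analysed on survey completers under missing-at-random; multiple imputation is only optional and logged app use has no role in handling non-response

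*Combined protocol and SAP*

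**What the plan says.** Section 3.2 takes usability, acceptability and cultural fit (secondary) and self-reported abstinence (exploratory) from the week 5 exit survey. Section 15.1 analyses them by regression on arm, "adjusting only for baseline measurements of the endpoint, if available, and the three stratification factors". A further analysis "also adjusts for any other covariates that differ across treatment groups at baseline with a p-value less than 0.20".

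On non-response, 15.1 Missing Data states: "All observed data will be utilized in the analyses, with missing data being assumed to be missing at random". It continues: "We will compare subjects with and without missing data in order to identify baseline covariates associated with missing data". Then: "Sensitivity analyses of the secondary/exploratory endpoints using multiple imputation may be considered depending on the amount of missingness". No trigger, imputation model or auxiliary variable is given, and no rule says how a missing abstinence answer is counted. The same paragraph says that an intent-to-treat analysis needs complete data on every subject.

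The app log is described in section 5.2 as "Any and all interactions with the app including days and frequency of use each day". The primary analysis in 15.1 uses it for all randomised participants and takes those who do not complete the week 5 survey to be non-users after their last launch.

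**The concern.** The study hypothesis in section 1.1 is that the tailored app will be rated higher on feasibility and acceptability, so these endpoints carry a claim even though they are secondary. For the app ratings, the main analysis is in effect a complete-case regression on arm and three binary factors. It is sound only if, within those strata, answering the survey is unrelated to the rating.

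That is doubtful for a survey about an app. Someone who stops using it may be less likely to answer, to rate it well and to have quit. The plan itself links survey non-completion to disengagement in its primary analysis. The planned comparison of completers and non-completers covers baseline covariates only. The adjusted analysis picks covariates by arm imbalance, not by their relation to missingness. The variable most likely to make missing-at-random credible is therefore collected but not assigned to that purpose.

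At stake are the absolute ratings and quit rates that a feasibility study hands to the next trial and, under some mechanisms, the comparison between arms.

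**Working it through.** **The plan's own figure.** The only power statement (15.2) concerns the primary endpoint: rates 35 and 38.15, 58 per arm, two-sided 0.05. SE = √((35 + 38.15)/58) = 1.123; 3.15/1.123 − 1.960 = 0.845; Φ(0.845) = 0.80. It reproduces and is unaffected by this point. No figure is given for the exit-survey endpoints.

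**Inputs.** From the documents: 58 per arm (15.2) and an 8% quit rate from earlier testing of the standard app (2.2), used as an illustration. Assumed, because the documents give no values: response of 60% to 90%, usability SD 20, correlation ρ of 0.3 to 0.5 between log use and score, and response logistic in standardised log use z with slope 1.0 or 1.5.

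**Mean ratings.** Excess of the completer mean = 20 × ρ × m, where m = E[z | responds] = ∫z p(z)φ(z)dz / ∫p(z)φ(z)dz and p(z) = 1/(1 + exp(−(a + bz))), with a set to give the response rate.

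| Response | Slope b | m | ρ = 0.3 | ρ = 0.5 |
|---|---|---|---|---|
| 80% | 1.0 | 0.173 | 1.0 | 1.7 |
| 80% | 1.5 | 0.227 | 1.4 | 2.3 |
| 60% | 1.0 | 0.332 | 2.0 | 3.3 |
| 60% | 1.5 | 0.427 | 2.6 | 4.3 |

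**Arm difference.** Bias = 20 × (ρ_T m_T − ρ_S m_S), for tailored and standard arms.

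- Same ρ and m in both arms: zero.
- Same mechanism, but tailoring raises use, so m differs slightly: simulations gave a bias of 0.3 to 0.8 points at 60% response.
- ρ of 0.5 in one arm and 0.2 in the other: 20 × 0.3 × m = 2.0 to 2.6 points at 60% and 1.0 to 1.4 at 80%, in either direction.

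**Quit rate.** If every non-responder smokes, the completer rate is 8%/(1 − attrition): 8.9%, 10.0%, 11.4% and 13.3% at 10%, 20%, 30% and 40%. With 8% true in both arms and attrition of 20% (tailored) versus 40% (standard), completers show 10.0% versus 13.3%, a spurious −3.3 points. With equal attrition the ratio of the two rates is unchanged.

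**Does logged use help?** In a separate simulation (400,000 participants, rating SD 15, ρ = 0.4, about 60% response, no true effect), completers averaged 71.9 against a true 70.0; weighting on use gave 70.0. Quit rates were 8.7%, 6.9% and 6.9% in the same order. With response depending more steeply on use in the standard arm, the completer difference was −1.9 against a true 0.0, and weighting gave 0.0. The weights were the true response probabilities, so this is a best case. With completely random non-response there was no bias.

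**Does it help at 58 per arm?** I simulated 1,500 trials per setting at about 60% response, with SD 20, a true difference of 5, ρ of 0.2 to 0.5 (equal or unequal by arm) and 25% higher use in the tailored arm. Imputing by arm on the strata and log use cut the bias in arm means from 1.9–3.9 points to 0.1 or less, and their root mean squared error (RMSE) from 3.9–5.1 to 3.4–3.8. For the arm difference, RMSE was 4.7–5.3 against 4.6–5.2 for completers. An 11-predictor within-arm model (five weekly launch counts, last day of use, three strata, nicotine dependence, cigarettes per day) mostly did worse than completers: about 5.5 against 4.7–5.4.

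**The case against.** Several stronger readings are tempting, and the documents do not support them.

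- A reader might infer that ratings and quit rates are overstated. That requires non-responders to be less satisfied or less often abstinent. The plan gives neither a response rate nor a mechanism.
- A reader might carry over the roughly 40% loss reported in section 2.3. Those were face-to-face studies in which transport was a major cause. This trial is remote, lasts 5 weeks, sends reminders (5.2) and pays for the survey and for completing all procedures (11.4). Hence the range shown here.
- A reader might say that the logs are excluded. They are unassigned: multiple imputation is named without its predictors. Their coverage also depends on each participant downloading the app and entering an ID, although the primary analysis treats use as known for everyone.
- A reader might say that the models use the strata alone. They also use a baseline value where available, and a secondary analysis adds covariates. For the app ratings this closes little of the gap.

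Precision also matters. With SD 20 and 35 completers per arm, the SE of a difference is 20 × √(2/35) = 4.8 points, so even the unequal-correlation bias at 60% response is roughly half an SE. The abstinence figures are an extreme bound on an exploratory endpoint.

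All of this stands, and it limits the size of the claim. It does not supply a pre-specified method. Nor does the statement that these endpoints follow the primary endpoint's approach, since no value is assigned to an unanswered survey.

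**Conclusion.** The point holds in conditional form. A completer analysis under missing-at-random is the stated method, its only sensitivity analysis is discretionary, and the most informative available predictor of non-response has no assigned role. If non-responders are less engaged, absolute ratings may be too high by about 1 to 2 points at 80% response and 2 to 4 at 60%. A true 8% quit rate may read as 8.9% to 13.3% at 10% to 40% attrition, the extreme case in which all non-responders smoke. These sizes rest on the assumed SD, correlation, response slopes and response rates.

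Bias in the comparison between arms is possible, not shown. It needs response, or its link with liking or quitting, to differ by arm; with a shared mechanism it is small, and with random non-response there is none. The primary endpoint, its power and the sample size are untouched. As the endpoints are secondary and exploratory, this is a worthwhile improvement and not a threat to the trial's main result.

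**What to change.** In 15.1 Missing Data, replace the optional sentence with a pre-specified imputation (or inverse-probability weighting) analysis of the exit-survey endpoints:

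- Run it by arm, with the three stratification factors and one summary of logged use, such as log(1 + total launches).
- Use logged use only as an auxiliary variable. It arises after randomisation and may be affected by arm, so it should not be a covariate in the outcome model.
- Report the result beside the completer analysis.
- For abstinence, also report missing-equals-smoking over all randomised participants, labelled as a bound.
- Keep the model small and avoid the 11-predictor version. At 8% there would be about 0.08 × 58 = 4.6 quitters per arm, so name a fallback for abstinence, such as use alone or weighting, in case the logistic imputation does not converge.

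The cost is modest programming on data already collected, added modelling assumptions and slightly wider intervals for the arm difference. Data collection, sample size and the primary analysis stay as they are.

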15.0 Statistical Considerations

15.1 Data Analysis Plan:

No blinding of the investigative team will occur.

General Approach

All statistical analyses will be performed using SAS (version 9.4) or R (latest version, R Core Team). All statistical tests will be two-sided and a significance level of 0.05 will be used. Proper transformation such as the logarithm transformation will be used to approximate normality for

MEDICAL PROTOCOL (HRP-590)

PROTOCOL TITLE: QuitGuide for American Indians: Aims 2 & 3

VERSION DATE: 11-16-2022

the outcome variables. All analyses will be completed using intent-to-treat principle unless otherwise noted.

Describing the Study Population

Baseline characteristics will be summarized for all participants and by study arm to identify any treatment group imbalances post-randomization. This will include household income, education level, traditional tobacco use, cultural identity, multiple tobacco use, quit readiness, nicotine dependence and CPD. Continuous variables will be summarized using mean, standard deviation, median and range, and compared between study arms using Student's t-tests or Wilcoxon rank-sum tests, as appropriate. Categorical variables will be summarized using frequency and percentage, and compared between study arms using Chi-square or Fisher's exact tests, as appropriate.

Primary Endpoint Analysis

The primary endpoint is the frequency of app use initiated by the participant. The number of times the app is initiated per day will be measured using data from Smokefree.gov. If a participant does not use the app on a particular day, Smokefree.gov records this as non-use or 0 for that day. The total number of times will be summarized for analysis by totaling the number of times the app is initiated from randomization to 5 weeks post-randomization.

Primary Analysis

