Our sample size is based on the primary outcome, frequency of app use initiated by the participant during the 5-week period. Using a two-sided, two-sample test for Poisson rates, a total of 116 participants (n=58 in the tailored group and n=58 in the non-tailored group) will allow us to achieve 80% power to detect a difference in frequency of app use between the groups of 3.15 assuming a rate of 35 (1 time per day over the 5 weeks) in the non-tailored group and an alpha of 0.05. This sample size is in alignment with other mHEALTH-related smoking cessation feasibility studies.^{36, 50}

15.3 Statistical Analysis:

See above.

MEDICAL PROTOCOL (HRP-590)

PROTOCOL TITLE: QuitGuide for American Indians: Aims 2 & 3

VERSION DATE: 11-16-2022

15.4 Data Integrity:

PI will periodically check for completeness as well as outliers or unusual values

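### The 80% power for a 3.15-launch difference in section 15.2 holds only under Poisson variance, a condition that the section does not state, justify or vary although 15.1 plans for departures from it

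*Combined protocol and SAP*

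**What the plan says.** The primary endpoint is each participant's total number of app launches from randomisation to five weeks.

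- **Power (15.2).** The sample size is derived "Using a two-sided, two-sample test for Poisson rates", with two-sided alpha 0.05 and 58 per arm, to "achieve 80% power to detect a difference in frequency of app use between the groups of 3.15 assuming a rate of 35" in the standard arm. No SD, dispersion value or second scenario is given. The one further remark is "This sample size is in alignment with other mHEALTH-related smoking cessation feasibility studies", which supports the size of the trial and says nothing about variance.
- **Model (15.1, Primary Analysis).** The analysis is a Poisson regression "with covariates for treatment group and the three stratification factors". The plan then says: "Assumptions about mean and variance will be evaluated and if over-dispersion is present, negative binomial regression will be used". Zero-inflated models may also be considered.
- **Who is counted, and how (15.1).** "This analysis will be performed using data for all participants who were randomized", "assuming non-use of app for those who did not complete the week 5 survey from the last day they launched the app". On a day without use, "Smokefree.gov records this as non-use or 0 for that day".

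**The concern.** A Poisson rate test fixes the variance at the mean. For that to hold, all participants, or all participants within a stratum once the model adjusts, must share one underlying launch rate for the whole five weeks. The endpoint rules in 15.1 work against this: someone who stops opening the app stays in the analysis with a low total, and people may differ in how often they open an app. The plan foresees over-dispersion when it chooses the model but not when it states power.

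Section 15.2 is the only place that says what the primary comparison can detect. If the variance is larger than Poisson, a non-significant result would be read as carrying a 20% type II error against 3.15 launches when the true figure is higher.

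**Working it through.** **Inputs from 15.2:** 35 launches in the standard arm, difference 3.15 (so 38.15 in the tailored arm, ratio 1.09), n = 58 per arm, two-sided alpha 0.05, power 80%. All dispersion and stopping values below are assumptions, because the documents contain none.

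**1. Reproduce the stated figure.**
- n per arm = (1.96 + 0.8416)² × (35 + 38.15) / 3.15² = 57.9, so 58.
- SE of the difference = √(73.15/58) = 1.123. Power = Φ(3.15/1.123 − 1.96) = Φ(0.845) = 80.1%.
- Implied control SD = √35 = 5.9, a CV of 17%.

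Log-rate and square-root versions also give 80.1%, and simulated Poisson counts give 80.0%.

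**2. Let the variance be φ times the mean.** Power = Φ(3.15/√(φ × 73.15/58) − 1.96).

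| φ (assumed) | Control SD | SE | Power |
|---|---|---|---|
| 1 | 5.9 | 1.123 | 80% |
| 1.13 | 6.3 | 1.194 | 75% |
| 1.25 | 6.6 | 1.256 | 71% |
| 1.5 | 7.2 | 1.375 | 63% |
| 2 | 8.4 | 1.588 | 51% |

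**3. Early stopping alone.** Suppose a fraction p of each arm stops on a day spread evenly over days 0 to 34, counts are otherwise Poisson, and overall means stay at 35 and 38.15. A stopper contributes on average 17/35 of a full total, and the mean of (day/35)² is 391/1225 = 0.319. The squared CV of the underlying rates is c = [(1 − p) + 0.319p] / (1 − 18p/35)² − 1, and variance = mean + c × mean².

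| p (assumed) | c | Variance, standard / tailored | Power, comparison of means |
|---|---|---|---|
| 2% | 0.0070 | 43.6 / 48.3 | 71% |
| 5% | 0.0176 | 56.6 / 63.8 | 59% |
| 10% | 0.0357 | 78.7 / 90.1 | 45% |

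Simulations of the adjusted models in 15.1 give, at 5% and 10%, 58% and 39% with negative binomial and 61% and 48% with quasi-Poisson. The gap at 10% comes from the choice of model, not from variance alone.

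**4. What the stratification factors can recover.** This simulation uses 58 per arm, blocks of 2 and 4, eight equally likely strata (assumed) and 3,000 trials per case. The control SD is 8.4, which is variance twice the mean. Adjusted negative binomial power is 53%, 57%, 63% or 71% if the three factors explain 0, 25, 50 or 75% of the extra variation. It is 77% if they explain all of it (1,500 trials, strata not balanced by blocks). With purely Poisson data the same model gives 78%. The Monte Carlo standard error is about 1 point.

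**5. Detectable ratio under negative binomial.** Solve log RR = 2.8016 × √([1/35 + 1/(35·RR) + 2k]/58), with k = CV² − 1/35. For CV 0.25, k = 0.0339, the square root is 0.0458, log RR = 0.128 and RR = 1.14. CVs of 0.20, 0.25 and 0.5 give RR of 1.11, 1.14 and 1.29, or differences of about 3.8, 4.8 and 10.3 launches. Simulated power of the adjusted model at these ratios is 81%, 82% and 80%.

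**The case against.** Four points can be made for the plan.

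- **Section 15.1 already deals with over-dispersion.** It does so for the choice of model, and that stands. It does not restore the 80%. At mild dispersion the switch may not be triggered. With an assumed 5% Pearson test for dispersion and no covariates, a two-step simulation (20,000 trials) gives power of 76.5% at φ = 1.13 and 71.4% at φ = 1.25, with type I error of 5.7 to 5.8%. These are close to the figures above.
- **The strata may absorb the spread.** They may, in part. The test in 15.2 is unadjusted and takes no account of them. They help only as far as rurality, gender and age group explain launch totals, and the documents give no figure for that.
- **This is a feasibility trial.** Section 1.1 does speak of preliminary efficacy, and 15.2 also supports the size by comparison with similar studies. That is why 116 is left alone. But the plan chose a two-sided 0.05 test of the primary endpoint and stated its power, so the statement should match the analysis.
- **Every loss figure is assumed.** Correct. The omission is certain; its consequence is not quantified.

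A reader might infer that the trial is shown to be underpowered, or that more participants are needed. The documents do not support either, because they give neither a dispersion nor a stopping rate. Nor do they settle whether a zero-inflated model would recover the loss. Stopping on a random day gives mostly low totals rather than zeros, which makes it unlikely, but no such model was fitted here.

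**Conclusion.** The calculation in 15.2 is correct and its 80% is conditional. It applies if variance equals the mean, and it is lower for any early stopping or person-to-person variation that the stratification factors leave unexplained. The figure is sensitive: an SD of 6.3 instead of 5.9 already gives 75%, and 8.4 gives 51%. Those sizes rest wholly on assumed dispersion, and the true loss cannot be read from the documents. The sample size, the choice of models and the all-randomised target, which 15.1 already sets, are not in question. What needs correcting is an unconditional power statement that would otherwise govern how a non-significant result is read.

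**What to change.** Keep 116 participants and the models in 15.1. Add wording to 15.2 along these lines:

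> The 80% power for a difference of 3.15 launches applies only if the variance of the five-week total equals its mean. With 58 per arm, a control mean of 35 and two-sided alpha 0.05, a negative binomial comparison has 80% power for a rate ratio of about 1.11, 1.14 or 1.29 if the residual control CV is 0.20, 0.25 or 0.5. These CVs are illustrative assumptions.

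Larger CVs are optional: 0.75 and 1.0 give ratios of about 1.47 and 1.68. If Smokefree.gov can supply launch counts for existing users of the public app, which the documents do not say, their dispersion would be a better basis.

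In 15.1, state that the primary result will be interpreted through the confidence interval for the rate ratio, not as an 80%-power test of 3.15.

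This costs protocol wording only, with no added participants and no change of test. The downside is a less favourable stated detectable effect.

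As a separate minor item with no bearing on power, reconcile the ceiling of 116 consented at the UMN and AICAF sites (10.1) with the study-wide ceiling of 126 (23.1). Section 23.0 lists only those two sites, and accrual against the recruitment goal is a secondary endpoint (3.2).
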